A sample size of 113 subjects treated with CSF-1 for at least 6 weeks will have at least 95% probability of detecting adverse events that occur at a rate of 2.66% or greater.

Safety Analysis

All safety data will be analyzed using the safety set. Safety of CSF-1 compared to vehicle will be assessed by the review of all safety parameters.

Verbatim descriptions of AEs will be mapped to Medical Dictionary for Regulatory Activities (MedDRA) terms and be presented in a data listing. A treatment-emergent adverse event (TEAE) is any event not present prior to the initiation of the drug treatment or any event already present that worsens in either intensity or frequency following exposure to the drug treatment. TEAEs will be summarized by treatment group using frequency and percent for each system organ class (SOC) and preferred term (PT) within each SOC. The number of AEs, TEAEs, serious TEAEs, and TEAEs causing premature

discontinuation will be provided by treatment group. In addition, the frequency and percentage of subjects with at least one AE, at least one TEAE, and at least one serious TEAE will also be provided by treatment group.

Similar summaries will also be presented for TEAEs related to the study drug, by severity, and by study day of onset. When reporting the incidence of AEs, a subject will only be counted once if they ever experience an event within the SOC and ever experience the individual PT within each treatment group. Number of AEs by a set interval of time will be summarized for each interval. Or number of AEs will be summarized for set intervals of time..

Changes from baseline in BDCVA, LL-BDCVA, slit lamp biomicroscopy, fluorescein staining, IOP, and dilated indirect fundus examination will be summarized descriptively at each visit where performed by treatment group.

The categorical summaries for the loss of ≥ 0.2 logMAR from baseline (yes/no) and for the loss of > 0.2 logMAR (yes/no) in BDCVA and LL-BDCVA at each visit will also be presented and compared between treatment groups using Pearson chi-squared test or Fisher's exact test if any cell counts are less than 5.

Full details of the safety analyses will be specified in the formal Statistical Analysis Plan (SAP).

Summary of Known and Potential Risks and Benefits to Human Subjects

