4 STUDY OBJECTIVE

4.1 Primary Objective

The primary objective of the study is to evaluate the safety of CSF-1 compared with vehicle in presbyopic subjects.

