11 STATISTICAL HYPOTHESES AND METHODS OF ANALYSES

11.1 General Considerations

In general, quantitative/continuous data will be summarized using descriptive statistics (number of subjects [n], mean, standard deviation [SD], median, minimum, and maximum).

Qualitative/categorical data will be summarized using frequencies and percentages. Statistical testing, unless otherwise indicated, will be performed at a 2-sided 0.05 significance level.

For all variables, baseline is defined as the last measurement taken prior to the administration of the first dose of study drug. Change from baseline will be calculated as follow-up measure minus baseline measure.

Summaries and listings will be presented for all subjects, or safety set, as needed. Safety analyses will be conducted in the safety set.

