11.4 Sample Size

Approximately 170 subjects will be randomized into the study in a 2:1 ratio of CSF-1:vehicle [approximately 113 randomized subjects assigned to CSF-1 and approximately 57 subjects randomized to vehicle] completing at least 6 weeks of treatment. Any subjects treated beyond Visit 4 at the time of Protocol Amendment 2.0 approval will exit the study at the next scheduled visit. All subject data will be analyzed.

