11.6 Safety Analysis

All safety data will be analyzed using the safety set. Safety of CSF-1 compared to vehicle will be assessed by the review of all safety parameters.

Verbatim descriptions of AEs will be mapped to Medical Dictionary for Regulatory Activities (MedDRA) terms and be presented in a data listing. Treatment emergent AEs (TEAEs) is defined as any event not present prior to the initiation of the drug treatment or any event already present that worsens in either intensity or frequency following exposure to the drug treatment. TEAEs will be summarized by treatment group using frequency and percent for each system organ class (SOC) and preferred term (PT) within each SOC. The

number of AEs, TEAEs, serious TEAEs, and TEAEs causing premature discontinuation will be provided by treatment group. In addition, the frequency and percentage of subjects with at least one AE, at least one TEAE, and at least one serious TEAE will also be provided by treatment group.

Similar summaries will also be presented for TEAEs related to the study drug, by severity, and by study day of onset. When reporting the incidence of AEs, a subject will only be counted once if they ever experience an event within the SOC and ever experience the individual PT within each treatment group. The number of AEs as well as the incidence rate over the study period will also be summarized.

Changes from baseline in vital signs, BDCVA, LL-BDCVA, slit lamp biomicroscopy, IOP, and dilated indirect fundus examination and endothelial cell density will be summarized descriptively for at each visit by treatment group. Changes from baseline in endothelial cell density parameters will be tested between treatment groups using two-sample t-tests.

The categorical summaries for the loss of ≥ 0.2 logMAR from baseline (yes/no) and for the loss of > 0.2 logMAR (yes/no) in BDCVA and LL-BDCVA at each visit will also be presented and compared between treatment groups using Pearson chi-squared test or Fisher's exact test if any cell counts are less than 5.

Full details of the safety analyses will be specified in the formal Statistical Analysis Plan.

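### Section 11.6 tests change in endothelial cell density with a t-test that subtracts baseline but does not adjust for it, and leaves the variance assumption open; a baseline-adjusted model would be more precise, once it is settled that this measure is collected

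*Combined protocol and SAP*

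**What the plan says.** The primary objective (Section 4.1) is comparative: to "evaluate the safety of CSF-1 compared with vehicle in presbyopic subjects".

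For endothelial cell density (ECD), Section 11.6 says: "Changes from baseline in endothelial cell density parameters will be tested between treatment groups using two-sample t-tests". It names no covariate and does not say whether the pooled or the unequal-variance t-test is meant. Section 11.1 supplies the definitions: "baseline is defined as the last measurement taken prior to the administration of the first dose of study drug", and "Change from baseline will be calculated as follow-up measure minus baseline measure". The level is set there too: "Statistical testing, unless otherwise indicated, will be performed at a 2-sided 0.05 significance level". On allocation, Section 11.4 says: "Approximately 170 subjects will be randomized into the study in a 2:1 ratio of CSF-1:vehicle", that is, about 113 and 57.

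The other continuous changes in Section 11.6 (vital signs, BDCVA, LL-BDCVA, IOP) "will be summarized descriptively for at each visit by treatment group". BDCVA and LL-BDCVA also have a between-arm comparison, but a categorical one: loss of at least 0.2 logMAR, and loss of more than 0.2 logMAR, by chi-squared or Fisher's exact test at each visit.

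ECD appears only in Section 11.6. It is not among the safety measures in the Synopsis or Section 7.1, the safety endpoints in Section 11.3, or the Synopsis safety analysis. The visit procedures in Section 9.3.1 are redacted and the Appendix 1 schedule is not shown. Section 11.6 leaves full details to a formal SAP, and no SAP text in the document supplied changes the method.

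**The concern.** A change score cannot be computed without a baseline value, so any subject who enters this test has one. Subtracting it forces a slope of 1 between follow-up and baseline. When the true slope is below 1, subtraction over-corrects, and the arm difference varies more than it would if the slope were estimated. For a safety comparison with vehicle, a wider interval makes a real loss on CSF-1 harder to see.

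The unstated variance assumption is a second, separate matter. With 2:1 arms, a pooled t-test is sensitive to unequal variances. If the larger arm is the more variable, the test becomes conservative, which is unhelpful when looking for harm. If the smaller arm is the more variable, it becomes liberal.

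**Working it through.** **The plan's own figure.** The Synopsis sample-size statement says that 113 CSF-1 subjects "will have at least 95% probability of detecting adverse events that occur at a rate of 2.66% or greater". Check: 1 − (1 − 0.0266)^113 = 0.9525, so it reproduces. It concerns adverse events. The documents give no SD, effect size or power for ECD.

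**Inputs.** From the documents: n = 113 and 57, two-sided 0.05, change = follow-up − baseline. Assumed: equal SD at baseline and follow-up, the same slope and variance in both arms, one value per subject, and correlation rho of 0.5 to 0.9.

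**Precision.** In units of SD²:
- change score: 2(1 − rho)
- baseline as covariate: 1 − rho²
- ratio: (1 − rho²) / [2(1 − rho)] = (1 + rho)/2, a reduction of (1 − rho)/2

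| rho (assumed) | Change score | Baseline-adjusted | Ratio | Less variance | CI narrower by 1 − √ratio | Adjusted power where the change score has 80% |
|---|---|---|---|---|---|---|
| 0.5 | 1.00 | 0.75 | 0.75 | 25% | 13.4% | 89.9% |
| 0.7 | 0.60 | 0.51 | 0.85 | 15% | 7.8% | 86.0% |
| 0.9 | 0.20 | 0.19 | 0.95 | 5% | 2.5% | 82.0% |

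The power column uses the difference that the change-score test detects with 80% power: (1.960 + 0.842) × √(1/113 + 1/57) = 0.455 SD of change.

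**Chance baseline imbalance.** The standard error of the baseline difference is √(1/113 + 1/57) = 0.162 SD. With slope 0.7, a two-standard-error imbalance (0.325 SD) shifts the change-score difference by (1 − 0.7) × 0.325 = 0.097 SD. This is not an additional loss. At rho 0.7 the change-score variance splits as 0.60 = 0.51 + 0.3² = 0.51 + 0.09, and 0.09/0.60 is the 15% already in the table. The shift is also smaller than one standard error of the change-score difference, √0.60 × 0.162 = 0.126 SD.

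**Size of a pooled t-test if variances differ.** Assume a 1.5-fold SD ratio.
- CSF-1 more variable: true variance 2.25/113 + 1/57 = 0.0375. Pooled variance (112 × 2.25 + 56)/168 = 1.833, times (1/113 + 1/57) = 0.0484. The standard error is overstated by √(0.0484/0.0375) = 1.14.
- Vehicle more variable: true variance 1/113 + 2.25/57 = 0.0483. Pooled variance (112 + 56 × 2.25)/168 = 1.417, giving 0.0374. The ratio is √(0.0374/0.0483) = 0.88, so the standard error is understated.

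In 40,000 simulated normal trials per setting, the pooled test had size 2.7% in the first case and 8.3% in the second (8.4% on a repeat). The unequal-variance test stayed near 5% (4.7% to 5.0%). If the variances are equal, the choice does not matter.

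**The case against.** The t-test is valid. Randomisation makes the change-score difference unbiased, and its standard error already includes chance baseline imbalance. The gain depends on a correlation that the documents do not give, and at rho 0.9 it is only 2.5% of interval width. The sample size rests on adverse events, safety is judged by review of all parameters, and Section 11.9 makes no multiplicity adjustment, so descriptive summaries elsewhere are a coherent choice. All of this stands. It limits the point to efficiency and robustness.

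A reader might infer more, and the documents do not support it:
- **That baseline is unused.** Section 11.1 subtracts it. What is missing is adjustment for it as a covariate.
- **That ECD baselines are already collected.** No readable list includes ECD. Redaction and the missing schedule mean that collection can be neither confirmed nor excluded.
- **That the plan commits to a pooled test.** Section 11.6 does not say so, and the unequal-variance test is also a two-sample t-test. Nothing in the documents suggests a 1.5-fold SD ratio.
- **That 2:1 allocation causes the precision loss.** It does not; it matters only for the variance question.
- **That acuity has no comparison with vehicle.** The categorical logMAR-loss comparisons are planned.

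Any replacement must also say how eyes are handled. Section 11.2 analyses both eyes, and Section 9.1.6 says that there is no designated study eye.

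**Conclusion.** The point holds as an improvement to the stated method. Replacing the change-score t-test with a baseline-adjusted model would reduce the variance of the ECD arm difference by 25%, 15% or 5% at an assumed rho of 0.5, 0.7 or 0.9. This rests on equal SDs at the two times and on a common slope and variance across arms; under those conditions the model is, in large samples, never less precise than the change score. Stating a variance-robust method also removes the possibility of a pooled test with size near 2.7% or 8.3%, figures that need the assumed 1.5-fold SD ratio.

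The t-test is not biased or invalid, and the gain is small if rho is high. The whole point is conditional on ECD being measured, which the readable text leaves unresolved.

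**What to change.** 1. Reconcile ECD first. Either add it to the safety measures (Synopsis, Section 7.1) and endpoints (Section 11.3) with its visits, or remove it from Section 11.6.
2. If it is measured, replace the t-test in Section 11.6 and the SAP with a linear model of follow-up ECD on treatment and baseline ECD, with robust standard errors. Use the mean of the two eyes per subject, or both eyes with standard errors clustered by subject, and fix that choice before unmasking. Report the adjusted CSF-1 minus vehicle difference with its 95% CI.
3. Optionally, give the same adjusted difference and CI for IOP, BDCVA and LL-BDCVA at Week 6, as estimation without a formal test, beside the planned descriptives and the categorical logMAR-loss comparisons. This is a preference, not a correction.

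The cost is some wording in Section 11.6 and the SAP and a few lines of code. If ECD is already measured, no new data are needed. The small downside is a model-based estimate shown beside the raw means.

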A total of 309 subjects with presbyopia were randomized in NEAR-1 (155 CSF-1 and 154 vehicle) and 304 were randomized in NEAR-2 (154 CSF-1 and 150 vehicle). Participants were treated BID (with an interval of 2 or 3 hours between both doses) with 1 drop of CSF-1 in each eye, for a period of 15 days. Efficacy parameters (Best Distance Corrected Visual Acuity (BDCVA) at 40cm and 4m, as well as pupil diameters) were measured on day 1, 8 and 15 at various time points during these days. The primary and key secondary end-points were the percentage of subjects with a ≥ 3 -line (15-letter) gain, from baseline, in BDCVA at 40 cm (Precision Vision chart) and no loss in BDCVA ≥ 5 letters (ETDRS

chart at 4 m) in the study eye on Day 8, 1 hour post dose 1 (primary end-point) and on the same Day 8, up to 4h post dose 1. The other secondary endpoints were the same endpoints but measured on Day 1 (up to 6h post dose 1) and on Day 15 (up to 8h post dose 1).

In both NEAR-1 and NEAR-2 studies, CSF-1 showed a statistically significant superior effect compared to vehicle in all primary and key secondary endpoints (all time points on Day 8 [from 1 hour post-dose 1 to 2 hours post-dose 2]). The superiority of CSF-1 compared to vehicle, was also demonstrated on Day 1 and on Day 15. The pooled data of NEAR-1 and NEAR-2 showed a statistically significant superior effect in all time points on Day 1 and Day 15.

In both Phase 3 studies, the safety endpoints of Slit-Lamp Biomicroscopy, BDCVA, Intraocular Pressure, and Conjunctival Redness, changes from baseline were found to be comparable between the CSF-1 and vehicle groups. On a drop comfort scale from 0 (very comfortable) to 10 (very uncomfortable), mean scores were <2 at all timepoints, indicating that CSF-1 was well tolerated.

The current safety study is initiated to evaluate the safety of CSF-1, administered twice a day (BID) with an interval of 2-3 hours.

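### The two acuity-loss categories compared between arms differ only at exactly 0.2 logMAR, and neither counts an individual loss of 5 to 9 letters

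*Combined protocol and SAP*

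**What the plan says.** Section 11.6 (Safety Analysis), repeated in the Synopsis, sets two yes/no outcomes for BDCVA and LL-BDCVA at each visit: one "for the loss of ≥ 0.2 logMAR from baseline (yes/no" and one "for the loss of > 0.2 logMAR (yes/no". Both are to be "compared between treatment groups using Pearson chi-squared test or Fisher's exact test if any cell counts are less than 5". Neither place lists a smaller loss.

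Three other provisions bear on the point:
- The paragraph before this one in Section 11.6 plans a descriptive summary by arm and visit of "Changes from baseline in vital signs, BDCVA, LL-BDCVA, slit lamp biomicroscopy, IOP" and other measures. Section 11.1 gives the content of such a summary as "descriptive statistics (number of subjects [n], mean, standard deviation [SD], median, minimum, and maximum".
- Section 10.1 makes clinically relevant worsening of a finding a recordable adverse event.
- Section 11.6 leaves full detail to a separate SAP, which is not part of the document.

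**The concern.** A pair of cut-offs is useful when each picks out a different size of loss. Here both sit at two lines, and the second removes only the subjects who fall exactly on the boundary. Nothing is listed at one line. A subject who loses 5 to 9 letters of distance acuity is a non-event in both categories, the same as a subject who loses none.

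Section 3 says that pilocarpine at high concentrations can blur distance vision and that 0.4% does not affect it. A safety study of the drug should therefore be able to report how many subjects on each arm had a modest loss. As listed, the categorical analysis speaks only to losses of two lines or more, and it spends two tests on nearly the same question.

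**Working it through.** **Inputs from the documents.** About 113 CSF-1 and 57 vehicle subjects (Section 11.4); two-sided 0.05 (Section 11.1); Pearson chi-squared, or Fisher's exact test if any cell is below 5 (Section 11.6); no multiplicity adjustment (Section 11.9). Section 3 equates three lines with a "15-letter) gain, from baseline, in BDCVA at 40 cm", so one line is 5 letters.

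**Assumptions, because the documents give no figure.** One line is 0.1 logMAR, so a letter is 0.02. Acuity is scored by letter. One eye per subject is analysed. Change is normal with SD 0.06, 0.08 or 0.10 logMAR, and vehicle does not shift.

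**The plan's own figure.** The Synopsis gives at least 95% probability of seeing an adverse event with a true rate of 2.66% in 113 subjects. 1 − (1 − 0.0266)^113 = 0.9525, so it reproduces. It concerns adverse events and sets no target for the acuity comparisons.

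**Step 1: category rates.** With δ the mean worsening and half a letter (0.01) for rounding,

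P(loss ≥ c) = 1 − Φ((c − 0.01 − δ)/SD).

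The strict category is c = 0.22, the next letter up. For δ = 0.06 and SD = 0.08:
- c = 0.20: CSF-1 1 − Φ(0.13/0.08) = 5.2%; vehicle 1 − Φ(0.19/0.08) = 0.9%.
- c = 0.22: CSF-1 1 − Φ(0.15/0.08) = 3.0%; vehicle 1 − Φ(0.21/0.08) = 0.4%.
- c = 0.10: CSF-1 1 − Φ(0.03/0.08) = 35.4%; vehicle 1 − Φ(0.09/0.08) = 13.0%.

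**Step 2: exact power of the stated test.** Sum Bin(x; 113, p₁) × Bin(y; 57, p₀) over all tables (x, y) for which the chi-squared/Fisher rule gives p < 0.05. Each cell shows SD 0.06 / 0.08 / 0.10.

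| Mean worsening on CSF-1 | Loss ≥ 0.2 | Loss > 0.2 | Loss ≥ 0.1 |
|---|---|---|---|
| 0.04 (2 letters) | 0.000 / 0.005 / 0.079 | 0.000 / 0.000 / 0.026 | 0.635 / 0.545 / 0.415 |
| 0.06 (3 letters) | 0.000 / 0.084 / 0.265 | 0.000 / 0.006 / 0.138 | 0.981 / 0.904 / 0.773 |
| 0.10 (5 letters) | 0.329 / 0.838 / 0.862 | 0.013 / 0.518 / 0.735 | 1.000 / 1.000 / 0.997 |

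In every row the strict category has the least power of the three.

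**Step 3: what the descriptive summary would show.** The approximate 95% half-width for the arm difference in mean change is 1.96 × SD × √(1/113 + 1/57) = 0.318 × SD. That is 0.019, 0.025 and 0.032 logMAR, or about 1 to 1.6 letters. A mean shift of 2 or 3 letters would therefore be visible in the planned table.

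**Step 4: loss confined to some subjects.** As an illustration, let 20% of CSF-1 subjects lose 0.12 logMAR (6 letters) on average and the rest lose none. The arm mean then moves by 0.2 × 0.12 = 0.024, about one letter. With SD 0.06, losses of 5 letters or more occur in 0.8 × 6.7% + 0.2 × 69.1% = 19% against 7%. Power is 0.56 at ≥ 0.1 and below 0.01 at ≥ 0.2. With SD 0.08 the rates are 23% and 13%, and power is 0.36 against 0.04.

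A test of the mean difference, which is not planned, would do about as well. For SD 0.06 its standard error is √((0.0036 + 0.2 × 0.8 × 0.12²)/113 + 0.0036/57) = 0.0107, so power is Φ(0.024/0.0107 − 1.96), about 0.6. The 0.1 category is therefore not more sensitive than a comparison of means. It adds the number of subjects affected, which a one-letter mean difference does not convey.

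**The case against.** **A reader might infer that a smaller worsening would go unseen.** The documents do not support that. Section 11.6 reports acuity change by arm at each visit, Section 11.1 includes the mean, SD and range, and Section 10.1 captures clinically relevant worsening as an adverse event. Safety is also to be judged on all parameters together, not on these tests alone. What remains is narrower: the listed analyses neither count nor compare individual losses of 5 to 9 letters. Adverse-event recording depends on the investigator's view of relevance, so it does not replace a measured threshold.

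**A reader might also infer that a 5-letter row would put this trial on the same scale as NEAR-1 and NEAR-2.** Section 3 does give "no loss in BDCVA ≥ 5 letters" as part of the NEAR endpoints. That was one component of an efficacy composite, measured after dosing in a study eye. Here Sections 5.1 and 8.1.2 describe acuity assessed before the visit dose, Section 9.1.6 says there is no designated study eye, and Section 11.2 analyses both eyes. The visit procedures are redacted, so this rests on the visible text. For its BDCVA safety endpoint, NEAR reported change from baseline, which is already planned here. The case for the row is its use within this trial.

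**The redundancy depends on scoring.** Appendix 2, where the acuity method would be, is not shown. With whole-line scoring the cut-offs become two lines or more against three or more, which is a meaningful split. The one-line category would still be missing.

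**Low power for a small mean shift is not in itself a defect.** A threshold at 0.2 is meant to flag large individual losses, and at a 5-letter mean shift it has 33–86% power. That objection stands. The power figures show what a lower threshold would add and do not show that the existing one is wrong.

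**Conclusion.** The point holds as a modest gap in the listed categories. The two cut-offs differ only at equality, and losses of 5 to 9 letters fall into neither. On the assumptions above, a cut-off of 0.1 logMAR raises power from 0–8% to 42–64% for a 2-letter mean worsening, from 0–27% to 77–98% for 3 letters, and from 33–86% to about 100% for 5 letters. The SDs, the shifts, letter scoring and one eye per subject are all assumed, so these ranges are indicative only.

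The documents contain no contradiction or error on this point, and the separate SAP may already add detail. The change is worth making but is not essential.

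**What to change.** In Section 11.6, the Synopsis and the SAP, add a category for a loss of 0.1 logMAR or more (5 letters or more) in BDCVA and LL-BDCVA, with the same between-group comparison. Keep the strict 0.2 category as a count without a test. The number of tests then stays at 2 measures × 2 cut-offs = 4 per visit for each eye analysed, which matters because Section 11.9 makes no multiplicity adjustment. If acuity is scored in whole lines, state that, and state why the strict category is kept. Do not present the new row as comparable with NEAR.

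The cost is one extra row per table and no new data. The drawback is that a 5-letter change lies closer to measurement noise, so both arms will show higher rates: 7–18% on vehicle with no true shift, from 1 − Φ(0.09/SD). Randomisation makes that background equal in expectation, but the text should warn against reading either arm's rate alone.
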